##### At risk for high sedentary behavior (meets at least one of the following criteria):

- Primarily sitting, full-time desk job (more than 30 hours per week)
- Primarily sitting, part-time desk job (less than 30 hours per week) and reports sitting at least half of the time during nonwork days
- Does not work and reports sitting at least three-fourths of the time
- Reports no more than 6000 steps per day from a wearable activity monitor

##### Risk factor for adverse pregnancy outcome (APO; meets one of the following criteria):

- Nulliparity
- History of APO
- Pre-pregnancy BMI of 30 kg/m^2 or greater
- Age of 35 years or older

##### Medical record access:

- Plans to deliver at the University of Pittsburgh facility or willing to provide consent for medical record release of prenatal care and birth records

#### *Exclusion criteria*

##### Young or advanced maternal age:

- Younger than 18 years; older than 45 years

##### Chronic hypertension:

- Resting blood pressure of 140/90 mm Hg or greater or antihypertensive medication use

##### Pregestational diabetes:

- Type 1 or type 2 diabetes, prior to pregnancy

##### Contraindication to exercise:

- Serious medical conditions such as underlying cardiac disease, severe anemia, chronic bronchitis, poorly controlled hyperthyroidism, or seizure disorder

Severe mobility limitation:

- Self-report of inability to walk 2 blocks or climb a flight of stairs

No prenatal care provider clearance:

- Unable to obtain a signed permission form from a prenatal care provider to participate in the intervention

Other research intervention:

- Participating in another health-related intervention study that could affect study outcomes

Travel plans restricting participation:

- Plans to travel that limit ability to fully participate in the study protocol

## Statistical Considerations

### *Analytic Strategy for Aim 1 and the Exploratory Aim*

We will use Stata (StataCorp) for all analyses with an intention-to-treat philosophy. First, participant flow will be summarized using a Consolidated Standards of Reporting Trials diagram for randomized trials [53]. Second, descriptive statistics will be computed for variables by treatment group and time point. Third, the baseline measures will be compared between the 2 groups using independent samples *t* tests, Wilcoxon rank sum, chi-square, or Fisher exact tests, as appropriate. While significant differences are not expected, any found will be considered in sensitivity analyses. Next, main analyses will fit a series of linear mixed models with follow-up continuous outcomes as the dependent variable (eg, SED); intervention group (intervention or control), follow-up time (eg, second and third trimester), and group  $\times$  time as fixed effects; baseline value of outcomes as fixed-effect covariates; and a participant random effect to account for multiple observations from the same participant over time. Mean contrasts will estimate the between-group difference at each follow-up time point. Similar methods will be used for the other activity variables (eg, standing and steps). Analysis of the exploratory aim will use similar methods, with logistic regression for dichotomous outcomes (eg, APOs). We will first consider the use of multiple imputation to account for missing data, but we will perform additional sensitivity or exploratory analyses to ensure robustness and extend our findings, for example, complete-data-only or last-value-carried forward strategies for missing data.

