## Scientific Background

Cardiovascular disease (CVD) remains the number one health threat in women [1]. Adverse pregnancy outcomes (APOs), such as hypertensive disorders of pregnancy, gestational diabetes, and preterm birth, affect up to 20% of pregnant women and are recognized as major risk factors for latent and future CVD [2,3]. Though research to disentangle the contributions of prepregnancy risk factors from APOs on future CVD risk is ongoing, interventions that prevent APOs as a target for reducing CVD offer immediate and possibly long-term benefits. Effective preventative therapies, however, remain elusive [4]. Moderate to vigorous-intensity physical activity reduces APO risk [5,6], but less than 1 in 4 pregnant women achieve guidelines [7]. This likely reflects that pregnant women report unique exercise barriers such as fatigue, pain, medical restriction, and concern for the baby [8]. Therefore, more feasible lifestyle strategies to prevent APOs are needed.

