## Study Objectives

The SPRING study's specific aims are to (1) evaluate the effect of SPRING versus control on objectively measured SED (*primary outcome, hypothesized to decrease*), standing (*hypothesized*

*to increase), and steps per day (*hypothesized to increase*); (2) evaluate the feasibility and acceptability of SPRING, including recruitment, retention, outcome assessment rates, intervention fidelity, and program evaluation; and (3) estimate the preliminary effects of SPRING versus control on maternal-fetal health outcomes including composite APOs (hypertensive disorders of pregnancy, gestational diabetes, and preterm birth), maternal blood pressure and glucose, psychosocial outcomes, gestational age at birth, and infant birth anthropometrics.*

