## **Eligibility Criteria**

We recruit participants in their first trimester of pregnancy who are at risk for high levels of SED and who have at least 1 risk factor for APO. These criteria reflect an early gestational age when we can intervene meaningfully across pregnancy and higher SED appropriate for modification (ie, reduction) to reach the levels that we have found to be associated with better pregnancy outcomes [11]. The criteria of having at least 1 risk factor for APO relate to our long-term goal to test whether our intervention can reduce APO risk; therefore, we sought to evaluate feasibility and preliminary effects in this specific population. Lastly, to allow for our exploratory outcome assessment using prenatal records of maternal-fetal outcomes, participants are required to

consent to abstraction either through our affiliation with the University of Pittsburgh Medical Center or through separate medical record release if they are receiving prenatal care elsewhere.

Participants younger than 18 years or older than 45 years are excluded to avoid an inability to provide consent and more complicated pregnancies with advanced age, respectively. Those with preexisting hypertension or diabetes are excluded because existing management of these conditions could affect our study outcomes (eg, prenatal blood pressure and glucose test results). Any other contraindications to exercise during pregnancy or severe mobility limitation are also exclusionary since the intervention asks participants to increase standing and daily steps. We also require participants to receive clearance for participation in the intervention from their prenatal care provider as an additional safety precaution. Lastly, those participating in other interventional research that could confound our study outcomes are excluded to reduce bias or contamination.

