### *Sample Size Considerations*

The primary outcome of this study is a change in SED. Based on our pilot data that suggest lower SED protects women from APOs [11], we calculated sample size requirements assuming the following: a between-group SED difference of 1 hour (SD 56 minutes) per day, a 2:1 randomization ratio to enhance recruitment and increase program evaluation and feasibility data, 90% power, and  $\alpha=.05$ . This yielded a required sample size of 42 (28 intervention and 14 control). A final sample size of up to 53 (35 intervention and 18 control), inflated by 20%, was adopted to account for attrition.

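### Logistic regression is planned for APOs and other dichotomous outcomes with no sparse-data method: the composite will be imprecise, and rarer outcomes may often have no finite odds ratio.

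*Combined protocol and SAP*

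**What the plan says.** Under Analytic Strategy for Aim 1 and the Exploratory Aim, continuous outcomes get linear mixed models, and the exploratory aim follows similar methods, "with logistic regression for dichotomous outcomes (eg, APOs". No penalised or exact version is named, and nothing says what happens if an arm has no events. The one small-sample method in that section is for comparing baseline measures: "chi-square, or Fisher exact tests, as appropriate".

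Study Objectives gives the third aim as to "estimate the preliminary effects of SPRING versus control on maternal-fetal health outcomes including composite APOs", and defines the endpoint as "composite APOs (hypertensive disorders of pregnancy, gestational diabetes, and preterm birth". It does not say that each component will be modelled on its own.

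No expected number of APOs is stated. Scientific Background says that APOs "affect up to 20% of pregnant women". Eligibility Criteria enriches for risk by recruiting women "who have at least 1 risk factor for APO". Sample Size Considerations sets the size from sedentary behaviour: "A final sample size of up to 53 (35 intervention and 18 control), inflated by 20%, was adopted to account for attrition".

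**The concern.** With 2:1 allocation the control arm has at most 18 women, so few control events can be expected. If either arm has no events, the maximum-likelihood log odds ratio has no finite value. The plan's wording covers dichotomous outcomes in general, so outcomes rarer than the composite fall under the same rule.

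Two things are at stake. First, without a stated method the analyst would choose a fallback after seeing an empty cell. Second, discarding fits that fail is not neutral. The smaller control arm is the one more likely to be empty, so the tables lost are mostly those whose odds ratio would be infinite. The tables that remain then lean towards apparent benefit. Multiple imputation, the plan's first option for missing data, adds a practical problem: one imputed dataset with an empty arm leaves nothing finite to pool.

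**Working it through.** **Inputs.** From the documents: arms of 35 and 18 (maximum) or 28 and 14 (required number), and an APO rate of up to 20%. Every other risk below is an assumption. Using 28/14 assumes that birth outcomes are lost at the same 20% as the sedentary-behaviour measure. Records may be more complete than that.

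**The plan's own sample size.** Control n = (1 + 1/2) × (56 × (1.960 + 1.282) / 60)² = 13.7, so 14, with 28 in the intervention arm, total 42. Dividing by 0.8 gives 52.5, so 53 (35 and 18). The stated figures reproduce.

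**Expected composite events at 20%.** 53 × 0.20 = 10.6, of which 18 × 0.20 = 3.6 are in controls. For 42 women: 8.4, of which 2.8 are in controls.

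**Precision at 20% in both arms (true odds ratio 1).** SE of the log odds ratio = √(sum of 1/expected cell).
- 35/18: √(1/7 + 1/28 + 1/3.6 + 1/14.4) = 0.725, and exp(1.96 × 0.725) = 4.1.
- 28/14: √(1/5.6 + 1/22.4 + 1/2.8 + 1/11.2) = 0.818, and exp(1.96 × 0.818) = 5.0.
- Illustration: 7/35 versus 4/18 gives (7 × 14)/(28 × 4) = 0.88, 95% CI 0.22 to 3.50.

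**Chance of no finite odds ratio.** With risks p₁ and p₀, this is 1 − [1 − (1 − p₁)^n₁] × [1 − (1 − p₀)^n₀]. The chance of an arm made up only of events is negligible here. For example, 20% in both arms at 35/18: 1 − (1 − 0.0004)(1 − 0.0180) = 1.8%.

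| Risk, intervention / control | 35/18 | 28/14 |
|---|---|---|
| 20% / 20% | 1.8% | 4.6% |
| 10% / 20% | 4.3% | 9.4% |
| 30% / 30% | 0.2% | 0.7% |
| 10% / 10% | 17% | 27% |
| 5% / 5% | 50% | 61% |

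**Effect of dropping failed fits (35/18, true log odds ratio 0).** At 10% the control arm is empty with probability 0.9^18 = 15.0% and the intervention arm with 0.9^35 = 2.5%, so the loss is lopsided. The mean maximum-likelihood log odds ratio over tables where it exists is −0.15 at 10% and −0.39 at 5%. The Firth estimate, which for two groups equals adding 0.5 to each cell, exists in every table. Its means are −0.03 and −0.15. The gain in bias comes from keeping every table.

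**Accuracy on the same tables.** Where maximum likelihood exists, the root mean squared error of the log odds ratio at 20% in both arms (35/18) is 0.78 for maximum likelihood and 0.69 for Firth. At 15% versus 30% it is 0.78 and 0.70.

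**An empty control arm.** 2/35 versus 0/18 has no finite maximum-likelihood value. Firth gives (2.5 × 18.5)/(33.5 × 0.5) = 2.8.

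**The case against.** The strongest reply is that the composite is the only APO endpoint the plan names, and for it failure is uncommon. The 20% is a general background figure. Recruiting women with a risk factor may raise it, although the exclusion of chronic hypertension and pregestational diabetes leaves the direction uncertain. At 30% failure is under 1%. This stands, and it rules out one reading a reader might infer: that the composite analysis is likely to break down. Its problem is imprecision, which no choice of estimator removes.

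A reader might also infer that the plan will fit a separate model for each component. The three conditions appear only as the definition of the composite. The general wording on dichotomous outcomes permits such models but does not promise them, and no component rates are given. The 10% and 5% rows are therefore conditional on two assumptions.

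A third reading, that a failed odds ratio would leave the next trial with nothing, is not supported either. Descriptive statistics by group are already planned, and the third aim includes several continuous outcomes.

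The accuracy gain from Firth is also modest. At 10% versus 20% (35/18), scoring maximum likelihood only where it exists and Firth on all tables gives 0.86 and 0.85. That comparison favours maximum likelihood, which is not charged for its failures, and on equal tables Firth was lower in every scenario run. Finally, making the risk difference the lead summary is a reporting preference. What survives is that the plan names no sparse-data method where one is cheap to name.

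**Conclusion.** The point holds as a minor, inexpensive improvement to an exploratory analysis. For the composite at the documents' 20%, expect about 8 to 11 events and an interval of the estimate divided and multiplied by 4 to 5. There is no finite odds ratio in about 2% to 5% of trials with equal risks, or 4% to 9% if the intervention halves the risk to 10%. For any modelled outcome with an assumed risk of 10% or 5% in both arms, the chance is 17% to 27% or 50% to 61%. Averaging only the fits that succeed would then favour the intervention spuriously, by 0.15 or 0.39 on the log scale at 35/18.

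These figures assume a two-group model without covariates. Adding baseline covariates in sensitivity analyses would make separation more likely. The primary outcome and the sample size are not affected.

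**What to change.** In Analytic Strategy for Aim 1 and the Exploratory Aim, replace logistic regression with Firth-penalised logistic regression for the composite APO and any other dichotomous outcome that is modelled, with treatment group as the only or nearly the only covariate. Add that event counts by arm and the risk difference with a score or exact interval will be reported alongside the odds ratio, not necessarily as the main summary. State that these results are estimates with intervals and not tests. Make the change before outcomes are seen.

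The cost is a different command, one added summary and a sentence or two of text. The odds ratio is generally pulled slightly towards 1: 3/35 versus 5/18 moves from (3 × 13)/(32 × 5) = 0.24 to (3.5 × 13.5)/(32.5 × 5.5) = 0.26. With unequal arms and an estimate near 1 it can move slightly the other way: 7/35 versus 4/18 goes from 0.88 to (7.5 × 14.5)/(28.5 × 4.5) = 0.85. Both shifts are small beside the width of the interval, which the change does not cure.

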### *Analytic Strategy Aim 2*

For the recruitment feasibility outcomes, we will calculate frequencies of recruitment method use and yields; rates of screening contacts, consent, eligibility, and randomization; reasons for ineligibility; and characteristics of enrolled participants. Benchmarks will be 42 (80%) for retention and 40 (95%) of the retained participants for valid outcome assessments. Intervention fidelity will be calculated based on intervention contacts with an overall average benchmark of 30 (85%) of each intervention contact completed. Quantitative or semiquantitative acceptability and program evaluation data will be summarized descriptively. Open-ended questionnaires will be analyzed using a constant comparison method to identify salient categories, themes, and

patterns via open coding, iterative review and codebook generation, code linking into similar categories, and final integration into themes [54].

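### Do the plan's own retention and valid-data benchmarks leave too few women for its stated 90% power?

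*Combined protocol and SAP*

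**What the plan says.** In the combined protocol and SAP, Sample Size Considerations names the outcome ("The primary outcome of this study is a change in SED") and assumes "a between-group SED difference of 1 hour (SD 56 minutes) per day", with 90% power, alpha of 0.05 and 2:1 allocation. It continues: "This yielded a required sample size of 42 (28 intervention and 14 control". Then: "A final sample size of up to 53 (35 intervention and 18 control), inflated by 20%, was adopted to account for attrition".

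Analytic Strategy Aim 2 sets the feasibility targets: "Benchmarks will be 42 (80%) for retention and 40 (95%) of the retained participants for valid outcome assessments".

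The main analysis, under Analytic Strategy for Aim 1 and the Exploratory Aim, is a linear mixed model of the second- and third-trimester values. It has the baseline value as a covariate and "a participant random effect to account for multiple observations from the same participant over time". On missing data it says: "We will first consider the use of multiple imputation to account for missing data". Complete-data analysis appears there as a sensitivity analysis.

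**The concern.** Read side by side, the two sections do not quite meet. The sample-size section needs 42 women, and its allowance is fully used by 20% attrition. The Aim 2 section accepts a further loss among those retained: 5% may lack a valid outcome assessment. That loss can really happen, because monitor data count only with at least 5 days of at least 10 waking hours of wear (Outcome Assessments). A woman can therefore stay in the trial and still have no primary outcome at a visit. A trial that meets every benchmark would have 40 such outcomes and not 42.

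Two labels add to the impression of faulty arithmetic. Raising 42 by 20% gives 50.4, not 53. And 42 of 53 is 79.2%, just under the 80% printed beside it.

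At stake would be a power statement that the trial's own targets cannot support, and an inflation rule that might be carried into a larger trial.

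**Working it through.** **Inputs.** Difference 60 min/day, SD 56 min/day, power 90%, alpha 0.05, ratio 2:1, required 42 (28 + 14), randomised 53 (35 + 18), all from Sample Size Considerations. Retention 80% and valid data 95% of those retained, from Analytic Strategy Aim 2. The plan does not state sidedness; two-sided reproduces its figure, while one-sided gives 36.

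**1. Reproduce the plan's figures.** With twice as many women on intervention as on control, the normal approximation gives

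control n = (1 + 1/2) × (1.960 + 1.282)² / (60/56)² = 1.5 × 10.51 / 1.148 = 13.73, rounded up to 14.

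Intervention is then 28 and the total 42, as stated. Allowing for 20% attrition: 42/0.8 = 52.5, rounded up to 53. By arm, 28/0.8 = 35 and 14/0.8 = 17.5, rounded up to 18. Both arms match the plan, so it divided by 0.8.

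**2. Apply the benchmarks.** 53 × 0.80 = 42.4, given as 42. Then 42 × 0.95 = 39.9, given as 40. Covering both losses in full would need 42/(0.80 × 0.95) = 55.3, or 56 randomised.

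**3. Power at 40, by the plan's own method.** Power = Φ(60 / (56 × √(1/n₁ + 1/n₂)) − 1.960). A two-sample t test (noncentral t) is shown for comparison.

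| Intervention / control | Standardised difference | Normal approximation | t test |
|---|---|---|---|
| 28 / 14 (total 42) | 3.273 | 90.5% | 89.1% |
| 26 / 14 (total 40) | 3.232 | 89.8% | 88.3% |
| 27 / 13 (total 40) | 3.174 | 88.8% | 87.1% |

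Like for like, losing two women costs 0.7 to 1.7 points by the normal approximation (90.5 − 89.8 and 90.5 − 88.8) and 0.8 to 2.0 by t test (89.1 − 88.3 and 89.1 − 87.1). Against the nominal 90%, the plan's own method falls short by 0.2 to 1.2 points. A gap of 2 to 3 points appears only if the t-test power at 40 is set against a 90% target derived from the normal approximation. That mixes two methods.

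**4. What a t test would need.** At exactly 2:1, 45 women (30/15) are needed, giving 91.2%. Without forcing the ratio, 43 women (28/15) give 90.5%. The planned 35/18 is not exactly 2:1 either.

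**5. Effect of the planned baseline adjustment.** The calculation takes no credit for it, and the plan gives no correlation, so this step is an assumption. At 27/13 by t test:

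| Residual SD (min) | Power |
|---|---|
| 56 (no gain) | 87.1% |
| 53 | about 90.5% |
| 50 | 93.4% |

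A fall from 56 to 53 is 3/56 = 5.4%. If 56 is the SD of follow-up values, the residual SD is 56 × √(1 − r²), and 53 needs a baseline/follow-up correlation of √(1 − (53/56)²) = 0.32. If 56 is the SD of change and the variances are equal, the residual SD is 56 × √((1 + r)/2), which is 53 or less for any correlation up to 2 × (53/56)² − 1 = 0.79. If 56 is already a residual SD, there is no further gain.

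**The case for a change.** The strongest reply is that the mismatch is in print and costs only wording to correct. The allowance does omit a loss that the plan itself tolerates, and every power figure at 40 lies below 90% unless a gain from adjustment is assumed. The sample-size section claims no such gain and does not say which SD the 56 minutes is. Group contrasts are planned at each follow-up visit, so valid data at each visit matter, and imputation does not recreate information that was never observed. Retention is a stated Aim 2 outcome, so a count of 42 beside 80% leaves it unclear whether 42 of 53 would pass.

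Much of this stands as description: the inflation leaves out the 5%, and the wording about 20% is loose. It does not show that the planned analysis misses its power by an amount that matters. The benchmarks are pass marks for feasibility. They do not define the Aim 1 analysis set, and they do not say whether a valid assessment means one follow-up visit or both. In the mixed model a woman with one valid follow-up visit still contributes, including one who leaves after the second trimester. Treating 40 as the analysed number imposes a complete-case reading that the plan keeps for sensitivity analysis. The retention count is a rounding of 42.4, and a reader can see what was meant.

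**Conclusion.** The counts are correct: 40 against 42 if both benchmarks are met exactly. On the least favourable reading (complete cases, no gain from baseline adjustment), power is 88.8% to 89.8% by the plan's own formula and 87.1% to 88.3% by t test, where 42 women would themselves give 89.1%. These figures rest on a two-sided 5% test, a true difference of 60 minutes, an SD of 56 minutes, and splits of 27/13 or 26/14.

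For a pilot and feasibility trial, a difference of this size changes no stated decision, no analysis and no conclusion. Sample-size inputs of this kind are far less certain than two women in 42: by t test at 28/14, an SD of 50 gives 94.7% and an SD of 60 gives 84.6%. Describing 42/0.8 as a 20% inflation, and rounding 42.4 to 42, are clerical matters that any analyst will read correctly. No change to the plan is called for.
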